5.2.4 Eastern Cooperative Oncology Group (ECOG) performance score

ECOG score: as given on the eCRF.

ECOG score change from baseline to last visit of last course = ECOG score at last visit of the last course – ECOG score at baseline. See also section [6.4](#) for missing ECOG scores.

Categorical ECOG score change: The ECOG score changes from baseline score will be categorized on a three point categorical scale: deteriorated (-1), unchanged (0), and improved (1). Improvement or deterioration of performance status will require a decrease or an increase from baseline, respectively, of at least one point on the ECOG scale.

5.2.5 ECG/QTc

The following endpoints will be regarded for the ECG analysis.

- QTcF changes from baseline at each time point: the QTcF post baseline measurement obtained at time t minus baseline QTcF measurement.
- Absolute QTcF intervals at each time point.

The above endpoint will also be computed for the uncorrected QT interval, for the heart rate (HR), PR interval and QRS duration. The heart rate (HR) will be derived from RR intervals.

- Categories of QTcF values at baseline and maximum post baseline:
QTcF \leq 450 ms, 450 ms $<$ QTcF \leq 470 ms, 470 ms $<$ QTcF \leq 500 ms, and QTcF $>$ 500 ms (notable prolongation)
- Categories of QT values at baseline and maximum post baseline:
QT \leq 500 ms and QT $>$ 500 ms (notable prolongation)
- Categories of the QTcF increase from baseline to the maximum post-baseline value:
intervals for a given patient as QTcF \leq 30 ms, 30 ms $<$ QTcF \leq 60 ms, QTcF $>$ 60 ms, (the latter increase reflects a notable change)
- Categories of the QT increase from baseline to the maximum post-baseline value:
intervals for a given patient as QT \leq 60 ms and QT $>$ 60 ms (the latter increase reflects a notable change)

All endpoints derived for the QTcF interval will also be derived for the QTcB interval.

5.2.6 Adverse events

According to the BI standards, multiple recordings of AEs will be collapsed to episodes on the lowest level term and for each patient, all episodes with the same PT(SOC) will be condensed to one AE record using a worst case approach for all AE attributes including CTCAE grading. This AE record per PT (SOC) forms the basis for all standard AE analysis on the patient level. CTCAE grade will be displayed in AE listings. MedDRA levels for condensing will be SOC and PT. AE listings will in general display records. A listing of episodes and occurrences will be provided.

AEs with action taken 'discontinued' or 'reduced' will be considered as marked on the eCRF irrespective of seriousness. Hence this includes the non-serious AEs considered as 'other significant' by ICH E3. No type of AE has been predefined as 'significant' in the CTP.

Dose limiting toxicities (DLT) events will be identified by the relevant question on the eCRF.

5.2.7 Laboratory parameters

In this trial the original laboratory values will be converted into standard units and the CTCAE grades will be assigned to all parameters which have a CTCAE definition. For this study, the laboratory parameters and their functional groups, together with the direction of concern, which were to be recorded and which have a CTCAE criteria definition are:-

Haematology: Haemoglobin (HGB) (-), white blood cells (WBC) (-) and Platelets (-)

Differentials: Neutrophils (-) and Lymphocytes (-)

Electrolytes: Sodium (+ and -) and Potassium (+ and -)

Enzymes: AST (+), ALT (+), Alkaline Phosphatase (ALKP) (+), Troponin (TPONT) (+)

Substrates: Total bilirubin (+), Glucose (+ and -) and Creatinine (+)

Coagulation: International Normalised Ratio of prothrombin time (INR) (+) and Partial thromboplastin time (APTT) (+)

The signs + (-) means the above (below) the reference ranges.

It is important to note that these above described values are the only parameters that can be graded according to CTCAE criteria. The other parameters reported cannot be graded according to CTCAE criteria.

The change of the laboratory value will be calculated for all laboratory parameters from the baseline to the end of the treatment for the whole treatment duration. No post-study laboratory values will be considered.

Worst lab value and its CTCAE grade (highest CTCAE grade) over all courses will be calculated for each laboratory parameter specified above.

The last lab value on treatment is the lab value of the last visit of the last course of each patient.

The change of the CTCAE grade of the lab value will be calculated

- from baseline to the last lab value on treatment
- from baseline to the worst value on treatment

Note: For calculating the change in CTCAE grade from baseline/ pre-dose level, patients with a CTCAE grade of -9 at baseline will be reviewed on a case-by-case basis. If there is no evidence that the corresponding laboratory value is of clinical significance, these values will be changed to -7 and treated as a CTCAE grade of 0 for analyses. All other values with CTCAE grade -9 will be regarded as CTCAE grade -8. Values with a CTCAE grade of -8

will either be removed from analyses concerning determination of baseline and worst CTCAE grade or if needed the category “not covered by CTC criteria” will be included. Values with CTCAE grades of -7 and -8 will be displayed in two separate listings.

In a similar manner, patients with a CTCAE grade of -1 will be reviewed on a case-by-case basis. For uric acid, values with CTCAE grade -1 will be regarded as either CTCAE grade 3 or CTCAE grade 1, depending on whether accompanied with physiological consequences (grade 3) or not (grade 1). A listing of the laboratory values with an assigned grade of -1 will be provided together with the re-assigned grade.

5.3 OTHER ENDPOINTS

5.3.1 Demographics and baseline characteristics

Number of previous systemic anti-leukemia therapies: Derived from PSYSTETHER page in the eCRF

Number of previous anti-leukemia radiotherapies: Derived from PRADIOOTHER page in the eCRF

Previous systemic anti-leukemia therapies that have the same start date and end date will be counted as a single anti-leukemia therapy. Previous therapies with the same compound but different start dates or end dates will be counted separately. These rules apply even in case of overlapping or time-adjacent dates.

With respect to previous radiotherapies the same rules apply as for systemic anti-leukemia therapies.

Time since last systemic anti-leukemia therapy [months]: = (date of informed consent - end date of the last systemic anti-leukemia therapy + 1 day) [days] / 30.

Time from first cytological diagnosis [years]: = (date of informed consent - date of first cytological diagnosis + 1) [days] / 365.25)

Age at the first Cytological diagnosis [years]: = (date of first cytological diagnosis – birth date+1)[days] / 365.25)

Secondary AML: Secondary AML is yes if the respective answer on the eCRF page is given. Otherwise Secondary AML is no and the patient is considered to have de novo AML.

Karyotype is considered ‘complex’ if cytogenetics are available (cytogenetics = yes on the eCRF) and the corresponding specification equals 2. It is considered ‘normal’ if cytogenetics are available and specification equals 1. It is considered ‘neither’ if cytogenetics are available and specification equals 2. Otherwise it is considered missing or not evaluable.

Findings for molecular genetics (e.g. t(8,21), inv16 and NRAS gene mutation) and the WHO classification of AML and related neoplasms will all be taken directly from the corresponding question on the eCRF page.

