4. CHANGES IN THE PLANNED ANALYSIS OF THE STUDY

- An additional comparison of objective response rates based on a Bayesian approach has been added.
- Blood products uses have been added as another endpoint in order to reflect supportive care requirements.
- The definition of relapse-free survival and remission duration has been changed. The definition now includes patients who have best response of CR or CRI and not only patients with CR in order to correct a misprint in the CTP.
- Genetic groups have been defined and the analysis of overall response, event-free survival and overall survival in these subgroups has been added.

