7.1 DEMOGRAPHIC AND OTHER BASELINE CHARACTERISTICS

Standard descriptive analysis and summary tables will be presented for all patients of the treated set by treatment group. At the report planning meeting it will be decided which additional variables will be tabulated in chapter 15 or the interim section of the CTR.

Disposition of patients

Standard descriptive analysis of the disposition will be provided.

If applicable, the number of patients who will continue treatment after database lock will be reported in the disposition table, separately.

Additionally, patients with discontinuations of the trial medication due to DLT will be listed by treatment and the reasons will be given. Listing of all patients with dose changes will be provided.

Important protocol violation

A table or listing of patients with protocol violations will be created.

Demographics and baseline characteristics

Standard descriptive analysis of the disposition will be provided.

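### SAP 5.3.1 derives both 'complex' and 'neither' karyotype from eCRF code 2, so the baseline karyotype table cannot be derived reliably as written

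*SAP*

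**What the plan says.** The rule is in SAP 5.3.1, among the derived baseline characteristics. It has four parts:

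- 'Complex': cytogenetics are available "and the corresponding specification equals 2".
- 'Normal': "It is considered ‘normal’ if cytogenetics are available and specification equals 1".
- 'Neither': "if cytogenetics are available and specification equals 2".
- Everything else: "Otherwise it is considered missing or not evaluable".

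No order of precedence is stated. The eCRF code list is not reproduced in the protocol or the SAP.

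The variable is destined for the baseline tables. On these, SAP 7.1 says: "Standard descriptive analysis and summary tables will be presented for all patients of the treated set by treatment group". SAP 4 separately records, as a change to the planned analysis: "Genetic groups have been defined and the analysis of overall response, event-free survival and overall survival in these subgroups has been added". SAP 7.4.1 and 7.5 refer to Section 6.4 for the definition of those genetic groups.

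**The concern.** The conditions for 'complex' and 'neither' are identical, so the categories are not mutually exclusive and a code-2 patient belongs to both. This is an operative derivation rule. SAP 5.3.1 takes the molecular genetic findings and the WHO classification straight from the eCRF, but karyotype is computed, so an error in the rule goes directly into the output.

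What is at stake is the reader's view of prognostic balance. Protocol 1.1 describes genetic alterations in the leukaemic cells as the leading prognostic factor in AML. Phase IIa randomises 43 patients per arm (Protocol 7.6.2). Protocol 7.5 names no stratification factor, and the logrank test in SAP 7.5 is unstratified. At that size chance imbalance is plausible, and the descriptive baseline table is where a reader would look for it. If the complex and 'neither' rows cannot be trusted, a real imbalance may appear in the wrong row or not appear at all.

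**Working it through.** No power, alpha or sample-size figure lies behind this point, so there is no plan figure to reproduce. The check is to apply the four written conditions to each possible code and then to set the result against the possible code lists.

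**Step 1: apply the rule as written** (cytogenetics available). 'First match' means that the first condition met fixes the label. 'Last match' means that a later condition overwrites an earlier one. Code 3 is an assumed third code.

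| Specification code | Conditions met | First match | Last match |
|---|---|---|---|
| 1 | normal | normal | normal |
| 2 | complex, neither | complex | neither |
| 3 | none | missing / not evaluable | missing / not evaluable |
| blank | none | missing / not evaluable | missing / not evaluable |

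Code 2 is the only code that can give either label. Under first match nobody can be labelled 'neither', and under last match nobody can be labelled 'complex'. One of the two rows is therefore always empty, whatever the code list.

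**Step 2: set this against the possible code lists.** Code 1 is taken as normal, as the SAP states. The assignment of the other results is assumed, because the documents do not give it.

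| Assumed eCRF coding | First match | Last match |
|---|---|---|
| complex = 2, neither = 3 | complex correct; neither goes to missing | complex labelled neither; neither goes to missing |
| neither = 2, complex = 3 | neither labelled complex; complex goes to missing | neither correct; complex goes to missing |
| both recorded as 2 | both labelled complex | both labelled neither |

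**Step 3: read across.** In each of the six cells at least one group is mislabelled or lost, and no cell fills all three categories correctly. Which group is affected, and how, changes from cell to cell.

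**Step 4: where the variable goes.** The available text shows it feeding only descriptive baseline summaries. The response comparison in SAP 7.4.1 (conditional power, odds ratio, Fisher's exact test, Bayesian posterior probabilities) uses no covariates. The sample size in Protocol 7.6.2 rests on response rates of 15% and 30% and does not involve karyotype.

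**The case against.** The strongest reply is that this is a one-digit slip. A programmer holding the eCRF code list would probably notice it, and SAP 7 gives a further safeguard: frequency tables are to show every possible category, and a missing row when values are missing, so an empty row or a swollen missing count would be visible. The text was also read from a PDF by a program, so a misread digit cannot be wholly excluded, although nothing points to one. The same rule applies to both arms, so it does not favour either by construction. The molecular findings and the WHO classification are unaffected.

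Most of this stands, and it is why the point is minor. It does not remove the need for a correction. The SAP is the specification, and a silent repair in the program would leave the code at odds with it. An empty row shows that something is wrong but not which patients belong in it.

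A reader might infer three stronger things, none of which the documents support:

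- **That 'neither' patients will be reported as complex, so that genetic balance between the arms is misreported.** The SAP gives 'complex' no priority. That outcome needs 'neither' to be coded 2 with first-match programming, or one code shared by both results with the same ordering. If 'neither' has its own code, those patients go to missing instead.
- **A head count of misclassified patients,** obtained by applying an assumed karyotype share to the 86 planned patients. The documents give no karyotype distribution, and the rule applies only where cytogenetics are available, so the denominator is unknown too.
- **That the error carries into the genetic subgroup analyses of response, event-free survival and overall survival.** SAP 4 says only that genetic groups have been defined and does not link them to this variable. Section 6.4 is not in the available text; that is not itself a fault in the plan, but it leaves the link unconfirmed.

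**Conclusion.** The point holds as an internal inconsistency in a derivation rule. The overlap on code 2 is certain from the SAP text, and nothing else in the available documents corrects it. No literal implementation populates 'complex', 'normal' and 'neither' correctly together, so the karyotype table by arm is unreliable as specified.

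The direction of the error depends on the eCRF code list and the programming order, and its size cannot be derived from the documents. The demonstrated reach is one descriptive baseline variable. The primary response comparison and the sample size are untouched, and any effect on the Section 6.4 subgroups is an open question. This is a low-severity correction that is worth making because karyotype bears on prognosis and the repair is almost free.

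**What to change.** 1. Correct SAP 5.3.1 against the eCRF code list so that 'complex', 'normal' and 'neither' each have their own code, and state the code for 'neither' explicitly. Keep missing or not evaluable for patients without a usable cytogenetic result.
2. Before database lock, cross-tabulate the derived karyotype against the raw specification code. Each code should map to one category, and no valid code should fall to missing.
3. Confirm whether the genetic subgroups in SAP Section 6.4 use this variable. If they do, apply the corrected derivation there as well.

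The cost is one SAP correction and one programming check. Data collection, sample size and the primary analysis do not change.

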5.3.2 Extent of exposure

Number of days of administration BI6727 [N]: Cumulative number of days with an administration of BI 6727.

Number of days of administration Cytarabine [N]: Cumulative number of days with an administration of cytarabine.

Number of courses initiated [N]: course initiated means: the patients received at least one administration of BI 6727 or cytarabine in the initiated course.

Cumulative total dose BI6727 [mg] = Sum of doses (administered dose of BI 6727) calculated across all courses

Total dose BI 6727 [mg] within a course = Sum of doses (administered dose of BI 6727) calculated per treatment course

Similar variables (cumulative total dose) will also be derived for LD-Ara-C.

Total exposure time to the trial drug [days] = date of first administration to MINIMUM (date of last trial drug administration of the last course + 21 days, death date if death occurs earlier than 21 days) + 1 day

Total observation time [days] = (last visit date (including follow-up) - date of randomisation + 1 day). Date of last visit does not include visit dates from follow-up where 'lost to follow-up' = yes.

The following two characteristic apply to BI 6727 only:

Number of patients with at least one dose escalation will be counted. A patient is considered to have at least one dose escalation if a dose escalation occurred at least once with BI 6727.

[figure not shown]
Number of patients with at least one dose reduction will be counted. A patient is considered to have at least one dose reduction if a dose reduction occurred at least once with BI 6727.

5.3.3 Other relevant observation related to safety

Vital signs will be recorded at baseline (including body weight), at each visit of each course and end of trial for each patient. Change from baseline to the end of the trial will be derived for each patient. Vital signs will be recorded also during infusion. If there are multiple measurements at a specific time point for vital signs, the last value will be taken.

Changes from baseline to the end of the trial = Parameter at end of the trial – parameter at baseline.

Percent change from baseline at the end of the trial = $100 * (\text{parameter at the end of the trial} - \text{baseline parameter}) / \text{baseline parameter}$.

6. GENERAL ANALYSIS DEFINITIONS

6.1 TREATMENTS

6.1.1 Treatment regimens / study intervals

The following study phases with short label, sort order and start date/time will be included in the treatment set-up in O*C.

Table 6.1.1: 1 Treatment regimens / study intervals

Short label (REGSHNM in E_REG) unblinded	Sort order (SORTREG in E_REG)	Start date (CRF)	Start time (CRF/ derived)
Screening	A	Date of informed consent	0:00:00
		If date of informed consent = date of administration then the start date for "Screening" will be derived as date of informed consent – 1 day	
150mg 1+15	BA	Date of administration of BI 6727 150 mg d1 + 15	Start time of administration of BI 6727 150 mg d1 + 15
200mg 1+15	BC	Date of administration of BI 6727 200 mg d1 + 15	Start time of administration of BI 6727 200 mg d1 + 15
250mg 1+15	BE	Date of administration of BI 6727 250 mg d1 + 15	Start time of administration of BI 6727 250 mg d1 + 15

Short label (REGSHNM in E_REG) unblinded	Sort order (SORTREG in E_REG)	Start date (CRF)	Start time (CRF/ derived)
300mg 1+15	BG	Date of administration of BI 6727 300 mg d1 + 15	Start time of administration of BI 6727 300 mg d1 + 15
350mg 1+15	BI	Date of administration of BI 6727 350 mg d1 + 15	Start time of administration of BI 6727 350 mg d1 + 15
400mg 1+15	BK	Date of administration of BI 6727 400 mg d1 + 15	Start time of administration of BI 6727 400 mg d1 + 15
450mg 1+15	BL	Date of administration of BI 6727 450 mg d1 + 15	Start time of administration of BI 6727 450 mg d1 + 15
500mg 1+15	BM	Date of administration of BI 6727 500 mg d1 + 15	Start time of administration of BI 6727 500 mg d1 + 15
550mg 1+15	BN	Date of administration of BI 6727 550 mg d1 + 15	Start time of administration of BI 6727 550 mg d1 + 15
150+Cy20	AA	Date of first administration of either BI 6727 150 mg d1 + 15 or Cytarabine 20 mg d1-10	Time of first administration of either BI 6727 150 mg d1 + 15 or Cytarabine 20 mg d1-10

Short label (REGSHNM in E_REG) unblinded	Sort order (SORTREG in E_REG)	Start date (CRF)	Start time (CRF/ derived)
200+Cy20	AC	Date of first administration of either BI 6727 200 mg d1 + 15 or Cytarabine 20 mg d1-10	Time of first administration of either BI 6727 200 mg d1 + 15 or Cytarabine 20 mg d1-10
250+Cy20	AE	Date of first administration of either BI 6727 250 mg d1 + 15 or Cytarabine 20 mg d1-10	Time of first administration of either BI 6727 250 mg d1 + 15 or Cytarabine 20 mg d1-10
300+Cy20	AG	Date of first administration of either BI 6727 300 mg d1 + 15 or Cytarabine 20 mg d1-10	Time of first administration of either BI 6727 300 mg d1 + 15 or Cytarabine 20 mg d1-10
350+Cy20	AI	Date of first administration of either BI 6727 350 mg d1 + 15 or Cytarabine 20 mg d1-10	Time of first administration of either BI 6727 350 mg d1 + 15 or Cytarabine 20 mg d1-10
400+Cy20	AK	Date of first administration of either BI 6727 400 mg d1 + 15 or Cytarabine 20 mg d1-10	Time of first administration of either BI 6727 400 mg d1 + 15 or Cytarabine 20 mg d1-10
Cy20	W	Date of first injection of Cytarabine 20 mg d1-d10	Time of first injection of Cytarabine 20 mg d1-d10

Short label (REGSHNM in E_REG) unblinded	Sort order (SORTREG in E_REG)	Start date (CRF)	Start time (CRF/ derived)
Post-trt	X	For BI 6727 monotherapy: Date of last administration	For BI 6727 monotherapy: Stop time of last administration + 1min.
		For BI 6727 combi with Cytarabine or Cytarabine mono: Date of last administration of BI 6727 or Cytarabine whichever is later	For BI 6727 combi with Cytarabine or Cytarabine mono: Time of last administration + 1min.
Post-study	Y	Date of last administration of trial medication (last treatment course) + 21 days.	0:00:00

6.1.2 Randomised treatment

Table 6.1.2: 1 Randomised treatment

Code unblinded (TPATT in E_TPATT)	Decode unblinded (NAME in E_TPATT)	Short decode unblinded (NAME in ADS.TPATT)	Sort order (L_CODE in E_TPATT)
A	Cytarabine, 20 mg bid (d1-d10)	Cy 20	01
C	BI 6727, 150 mg (d1+d15)	150mg1+15	08
E	BI 6727, 200 mg (d1+d15)	200mg1+15	09
K	BI 6727, 350 mg (d1+d15)	350mg1+15	12
L	BI 6727, 400 mg (d1+d15)	400mg1+15	13
M	BI 6727, 450 mg (d1+d15)	450mg1+15	14
N	BI 6727, 500 mg (d1+d15)	500mg1+15	15
O	BI 6727, 550 mg (d1+d15)	550mg1+15	16
AD	Cytarabine, 20 mg bid (d1-d10) + BI 6727, 150 mg (d1+d15)	150mg1+15+Cy	02
AE	Cytarabine, 20 mg bid (d1-d10) + BI 6727, 200 mg (d1+d15)	200mg1+15+Cy	03
AG	Cytarabine, 20 mg bid (d1-d10) + BI 6727, 250 mg (d1+d15)	250mg1+15+Cy	04
AI	Cytarabine, 20 mg bid (d1-d10) + BI 6727, 300 mg (d1+d15)	300mg1+15+Cy	05
AK	Cytarabine, 20 mg bid (d1-d10) + BI 6727, 350 mg (d1+d15)	350mg1+15+Cy	06
AM	Cytarabine, 20 mg bid (d1-d10) + BI 6727, 400 mg (d1+d15)	400mg1+15+Cy	07

6.1.3 Specification of treatments for analyses

Table 6.1.3: 1 Definition of the label of the analysing treatment period, analysis numbers, and the labels using for displaying in the tables, start date and end date.

Label of the "ATP" (ANALLBL)	Analysis number (ANALNO)	Label for the columns displayed in the tables (NWTRCD)	Start date	End date
Screening	5	Actual treatment (atrcd) ²	Date of informed consent	Start date of first treatment in course 1
Course 1 analysis	4	Initial treatment schedule ¹	Start date of first treatment in course 1	Start date of first treatment in course 2 or start date of the actual treatment "post-study"
Course 1 analysis	4	Total	Start date of first treatment in course 1	Start date of first treatment in course 2 or start date of the actual treatment "post-study"
All course analysis	3	Initial treatment schedule ¹	Start date of first treatment in course 1	Start date of actual treatment "post-study"
All course analysis	3	Total	Start date of first treatment in course 1	Start date of actual treatment "post-study"
Post-study	7	Initial treatment schedule ¹	Start date of actual treatment "post-study"	Date of Data Base Lock + 1 day

¹- use treatment specification of the initial treatment schedule defined in [Table 6.1.2: 1](#) and column 'Format for TPATT'

²- use treatment specification of the actual treatment defined in [Table 6.1.1: 1](#)

Note that death or lost to follow-up automatically ends the currently ongoing analysing treatment period for a patient.

